#### 6.3.4.2 Evaluation of Non-Target Lesions

Complete Response (CR): Disappearance of non-target lesions.

Progressive Disease (PD): Appearance of one or more new lesions and/or unequivocal progression of existing non-target lesions. It must be representative of the overall non-target disease rather than an increase in a single lesion.

Non-CR/Non-PD: Persistence of one or more non-target lesion(s).

#### 6.3.4.3 Evaluation of Best Overall Response

The best overall response is the best response recorded from the start of the treatment until disease progression/recurrence (taking as reference for progressive disease the smallest measurements recorded since the treatment started).

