#### 3.5.1 Evaluation:

- Patients will follow up 1 and 2 weeks after cell infusion for safety assessment and research studies as indicated on the **Study Calendar**. Response will not be measured at these visits.
- Patients will follow up 1, 2, and 3 months after cell infusion for safety assessment, research studies, and response evaluations.
- Patients with no response at the 3 month evaluation will come off-treatment and receive standard of care therapy.
- Patients with a partial or complete response at the 3-month evaluation will follow up at 4, 5, and 6 months for safety, response, and research evaluations.
- After the 6-month response assessment patients with partial response will receive standard of care therapy. Patients with a complete response will thereafter have follow-up every 3 months (+/- 30 days) for 2 visits, then every 6 months (+/- 30 days) for 2 visits (2 years of follow up total).
- Patients with disease progression at any time will come off treatment and receive standard of care therapy.

- Patients who come off treatment will follow up as required for gene transfer studies or as clinically indicated.

3.5.2 At each Response Evaluation, patients will undergo the following:

- Physical examination
- Chem 20 equivalent: (Sodium (Na), Potassium (K), Chloride (Cl), Total CO2 (Bicarbonate), Creatinine, Glucose, Urea nitrogen (BUN), Albumin, Calcium total, Magnesium total (Mg), Inorganic Phosphorus, Alkaline Phosphatase, ALT/GPT, AST/GOT, Total Bilirubin, Direct Bilirubin, LD, Total Protein, Total CK, Uric Acid).
- Complete Blood Count with differential and TBNK
- Toxicity assessment, including a review of systems.
- Serum, plasma, and peripheral blood lymphocytes.
- HSIL measurements and photographs will be taken for documentation of response.

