### **6.3.2 Disease Parameters**

Measurable disease: Measurable lesions are defined as those that can be accurately measured in at least one dimension as  $\geq 5$  mm. All measurements must be recorded in millimeters (or decimal fractions of centimeters).

Non-measurable disease. All other lesions (or sites of disease), including small lesions (longest diameter  $< 5$  mm), are considered non-measurable disease.

Target lesions. All measurable lesions will be identified as target lesions and recorded and measured at baseline.

Non-target lesions. All other lesions (or sites of disease) will be identified as non-target lesions and should also be recorded at baseline. Measurements of these lesions are not required, but the presence, absence, or in rare cases unequivocal progression of each will be noted throughout follow-up.

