### **6.3.3 Methods for Evaluation of Measurable Disease**

Lesions will be photographed, described in detail, and measured at each response evaluation. Measurements will be recorded in metric notation using a ruler or calipers. Baseline evaluations will be performed no more than 8 weeks before starting treatment.

The same method of assessment will be used to characterize each identified and reported lesion at baseline and during follow-up. Lesions will be documented by digital color photography at each response evaluation.

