### **6.3.4 Response Criteria**

#### **6.3.4.1 Evaluation of Target Lesions**

Complete Response (CR): Disappearance of all target lesions. No appearance of new lesions.

Partial Response (PR): A  $\geq 50\%$  decrease in the sum of the product of the longest perpendicular diameters of target lesions, taking as reference the baseline measurements. No appearance of new lesions. No increase of greater than 25% of any index lesion.

Progressive Disease (PD): A  $\geq 25\%$  increase in sum of the product of the longest perpendicular diameters of target lesions, taking as reference the smallest product on study (this includes the baseline product if that is the smallest on study). In addition to the relative increase of 25%, the sum must also demonstrate an absolute increase of at least 5 mm. (Note: the appearance of one or more new lesions is also considered progression).

Non-CR/Non-PD: Neither sufficient decrease to qualify for PR nor sufficient increase to qualify for PD, taking as reference the smallest product of diameters while on study.

Note: In the event of lesion regression with a residual abnormality of unclear significance, a biopsy may be obtained. If HSIL is present in the pathology specimen the response will be considered less than complete. If HSIL is not present the response will be considered complete.

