## 8 STATISTICAL CONSIDERATIONS

The primary objective of this phase I trial is to determine the safe dose level of E6 TCR T cells for the treatment of vulvar HSIL. Secondary objectives include an assessment of the clinical responses in subjects receiving this treatment and exploratory analyses of translational research endpoints.

This is a phase I trial with a standard 3+3 design and two dose levels. The maximum number of patients required to determine the MTD on this trial is 12. Six additional patients will be evaluated at the MTD, for a maximum intended enrollment of 18 patients. To allow for patients who enroll but are not evaluable for the primary endpoint and screen failures, up to 200 patients total may be enrolled.

The expected accrual rate is 10-15 patients per year. It should therefore take 1.25-2 years to complete accrual of patients.

The clinical responses in 12 patients tested at the MTD may be used in the design of a subsequent phase II trial.

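### Best overall response rests on one unconfirmed reading; a confirmed rate should be reported beside it before either informs phase II

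*Combined protocol and SAP*

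**What the plan says.** **Response rule.** Section 6.3.4.3: "The best overall response is the best response recorded from the start of the treatment until disease progression/recurrence". Section 6.3.5 dates a response from the first time the criteria are met. Neither section requires a second reading or a minimum duration.

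**Threshold.** Under 6.3.4.1, PR is a fall of at least 50%, a "decrease in the sum of the product of the longest perpendicular diameters of target lesions, taking as reference the baseline measurements". There must be no new lesion and no index lesion up by more than 25%. Progression is a rise of at least 25% from the smallest value, with a further condition: "In addition to the relative increase of 25%, the sum must also demonstrate an absolute increase of at least 5 mm".

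**What is measured.** Section 6.3.2: "Measurable lesions are defined as those that can be accurately measured in at least one dimension as" 5 mm or more. The second diameter has no minimum. All such lesions are summed: "All measurable lesions will be identified as target lesions and recorded and measured at baseline". Section 6.3.3: "Measurements will be recorded in metric notation using a ruler or calipers".

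**When.** Section 3.5.1 schedules response readings at months 1, 2 and 3. Patients not in response at month 3, and patients who progress at any time, leave protocol follow-up for standard care. "Patients with a partial or complete response at the 3-month evaluation will follow up at 4, 5, and 6 months".

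**Use.** Section 8: "The clinical responses in 12 patients tested at the MTD may be used in the design of a subsequent phase II trial". It does not say which response count is meant.

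**The concern.** A maximum taken over several noisy readings is biased upward, and a baseline that happens to read high adds to the bias. Confirmation is the usual guard, and here there is none. Photographs are taken at each evaluation, but no rule uses them to verify a response. Biopsy is optional and only settles whether an unclear residual abnormality counts as CR; it does not verify PR.

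The trial is uncontrolled, and section 1.2.1 puts spontaneous regression below 1.5% of patients per year. Almost any recorded response will therefore be read as a drug effect. At stake is the response rate at the MTD that section 8 offers for phase II design, where each patient in 12 is worth 1/12 = 8.3 percentage points.

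The plan also contains two notions of response. A patient in PR at month 2 but not at month 3 counts as a responder in 6.3.4.3 and as a non-responder for follow-up in 3.5.1.

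**Working it through.** **The plan's own figures.** Two dose levels x 6 = 12 patients to find the MTD; 12 + 6 = 18 in all; 6 + 6 = 12 at the MTD. These reproduce section 8. The documents state no response rate or reading error to reproduce.

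**How small an error suffices.** If both diameters shrink equally, a 50% fall in the product needs a fall of 1 - sqrt(0.5) = 29% in each, or about 1.5 mm on 5 mm. Take a true 5x5 mm lesion read 6x6 at baseline (36 mm2) and 4x4 once (16 mm2). The fall is 1 - 16/36 = 55.6%, which is PR. A correct next reading of 25 mm2 is up 25/16 - 1 = 56%, and up 9 mm2, which is progression. Best overall response stays PR.

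**Simulation of stable patients.** From the documents: the PR and progression rules, entry at 5 mm, readings at months 1-3, and counting stopped at the first progression. Assumed:
- independent normal error on each diameter, with fixed SD or proportional CV;
- rounding to 1 mm, with a minimum reading of 1 mm, so no false CR can arise;
- the absolute progression condition taken as 5 mm2. The protocol states it in mm although a sum of products is in mm2, and this needs reconciling.

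Each setting has 400,000 patients. Confirmed means PR at two consecutive readings.

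| True stable disease | Error | PR at any of 3 | Confirmed PR |
|---|---|---|---|
| 5x3 mm | SD 0.5 mm | 7% | under 1% |
| 5x3 mm | SD 1 mm | 35% | 8% |
| 5x5 mm | SD 0.5 mm | 0.4% | about 0.01% |
| 5x5 mm | SD 1 mm | 16% | 1.9% |
| 6x4 mm | SD 1 mm | 18% | 2.3% |
| 8x5 mm | SD 0.5 mm | 0.1% | about 0 |
| 8x5 mm | SD 1 mm | 8% | 0.6% |
| 10x6 mm | CV 15% | 4.4% | 0.2% |
| 10x6 mm | CV 20% | 13% | 1.3% |
| 20x10 mm | SD 1 mm | about 0 | about 0 |
| 20x10 mm | CV 20% | 12% | 1.2% |
| two 8x5 mm | SD 1 mm | 1.0% | about 0 |
| three 5x5 mm | SD 1 mm | 1.1% | about 0 |

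The progression stop matters. Without it, the unconfirmed rates at SD 1 mm are 40% (5x3 mm), 21% (6x4 mm) and 9% (8x5 mm).

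**Worst case for 12 patients.** If every MTD patient had one stable 5x5 mm lesion and SD were 1 mm, expected false responders are 12 x 0.162 = 1.9, and P(at least one) = 1 - (1 - 0.162)^12 = 88%. With confirmation, P(at least one) = 1 - (1 - 0.019)^12 = 21%.

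**The other error: true responders missed.** Same model, sustained true area reduction, with readings to month 6 for those in PR at month 3.

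| Baseline and error | True fall | Unconfirmed | Confirmed |
|---|---|---|---|
| 8x5 mm, SD 1 mm | 60% | 92% | 54% |
| 10x6 mm, CV 15% | 60% | 93% | 60% |
| 20x10 mm, SD 1 mm | 60% | 98% | 71% |
| 8x5 mm, SD 1 mm | 70% | 98% | 68% |
| 10x6 mm, CV 15% | 70% | 99% | 75% |
| 20x10 mm, SD 1 mm | 70% | 100% | 76% |

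The loss arises largely because noise around a shrunken lesion is read as progression before a second PR is recorded.

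**Visit spacing.** With 30-day months and the windows of 7 days either side in section 3.5, consecutive visits can be 30 - 14 = 16 days apart. Calendar footnote 9 in section 3.3 allows 14 days either side, which leaves 30 - 28 = 2 days. The two windows should be reconciled. A fixed minimum of three weeks would fit neither.

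**The case against.** The strongest case against has four parts.

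- **The size is assumed.** No reading error is documented. At SD 0.5 mm only the 5x3 mm case is material. In the same model at SD 1 mm, 74-79% of stable patients with a 5x3, 6x4 or 8x5 mm lesion are read as progressing by month 3, so the noise distorts more than response. This stands.
- **The vulnerable patient may be uncommon.** Section 1.2.1 calls multicentric disease common, and summing lesions dilutes error. A single small lesion is eligible after failed surgery (section 2.1.1), but nothing shows that it is typical. This stands for fixed error. It is weaker if error grows with lesion size, because a single 20x10 mm lesion at CV 20% still gives 12%.
- **Confirmation can do more harm than good.** For a 20x10 mm lesion at SD 1 mm there is almost no false PR to remove, yet 27 points of true 60% responses are lost (98% to 71%). This stands, and it rules out substituting the confirmed rate.
- **Little depends on it.** Response is secondary, section 8 says only that the data may be used, and the exact 95% interval for 2 of 12 is already 2-48%. Duration of response would show a one-visit PR as short. This lowers the weight of the point. It does not tell a phase II designer how many of the counted responses were seen twice.

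A reader might also infer that every patient has at least three chances to respond. The schedule does not support that: progressors leave earlier, and a patient not in response at month 3 has at most three readings.

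**Conclusion.** The gap is real. Best overall response can rest on one reading, and the plan gives no way to tell such a response from one seen again. Its size cannot be fixed from the documents. Under the stated assumptions, false PR ranges from about zero (large or multiple lesions with 1 mm error) to 35% (one 5x3 mm lesion, SD 1 mm), with 8-18% for one lesion of 8x5 to 6x4 mm at SD 1 mm.

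Three stronger readings are tempting and not supported:
- that ruler error would by itself produce this trial's response rate, which needs both an error size and a lesion mix that the documents do not give;
- that the confirmed rate is the correct one, when it misses a large share of true responders in the same model;
- that the primary conclusion is at risk, when dose finding uses DLTs only.

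What holds is narrower. The single rate as defined should not go into phase II design without a confirmed rate beside it.

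**What to change.** In 6.3.4.3 and section 8, report two response rates side by side:
1. best overall response as now defined;
2. confirmed response: CR or PR criteria met again at the next scheduled response evaluation, with no fixed minimum interval, dated from the first of the two evaluations.

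State that both go to the phase II design as the higher and lower readings, and that neither replaces the other. They are not formal bounds, since each can miss true responders. State also that the month-3 follow-up decision uses the month-3 reading, so its count may differ from either rate.

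The cost is a few sentences and one extra line in the results table. No visit is added and the follow-up rules stay as they are: a PR first seen at month 1 or 2 is read again a month later, and a PR at month 3 already leads to month 4. No first PR can arise at month 6, because only patients in response at month 3 are scheduled then. The downside is that the confirmed rate can be well below the true rate, which is why both must be shown.

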#### **For Patients with Measurable Disease (i.e., Target Disease)**

Target Lesions	Non-Target Lesions	New Lesions	Overall Response
CR	CR	No	CR
CR	Non-CR/Non-PD	No	PR
CR	Not evaluated	No	PR
PR	Non-CR/Non-PD/not evaluated	No	PR
Non-CR/Non-PD	Non-CR/Non-PD/not evaluated	No	Non-CR/Non-PD

PD	Any	Yes or No	PD
Any	PD*	Yes or No	PD
Any	Any	Yes	PD

* In exceptional circumstances, unequivocal progression in non-target lesions may be accepted as disease progression.
 
Note: Patients with a global deterioration of health status requiring discontinuation of treatment without objective evidence of disease progression at that time should be reported as “symptomatic deterioration.” Every effort should be made to document the objective progression even after discontinuation of treatment.
			

### 6.3.5 Duration of Response

Duration of overall response: The duration of overall response is measured from the time measurement criteria are met for CR or PR (whichever is first recorded) until the first date that recurrent or progressive disease is objectively documented (taking as reference for progressive disease the smallest measurements recorded since the treatment started).

Duration of overall CR: The duration of overall CR is measured from the time measurement criteria are first met for CR until the first date that progressive disease is objectively documented.

Duration of overall non-CR/non-PD: Non-CR/non-PD disease is measured from the start of the treatment until the criteria for progression are met, taking as reference the smallest measurements recorded since the treatment started, including the baseline measurements.

## 6.4 TOXICITY CRITERIA

Careful evaluation to ascertain the toxicity, immunologic effects and anti-HSIL efficacy of the treatment regimens will be performed. This study will utilize the CTCAE version 4.0 for toxicity and adverse event reporting. A copy of the CTCAE version 4.0 can be downloaded from the website <http://ctep.cancer.gov>. All appropriate treatment areas should have access to a copy of the CTCAE version 4.0. A copy of the CTCAE version 4.0 can be downloaded from the CTEP web site ([http://ctep.cancer.gov/protocolDevelopment/electronic\\_applications/ctc.htm#ctc\\_40](http://ctep.cancer.gov/protocolDevelopment/electronic_applications/ctc.htm#ctc_40)).

## 7 SAFETY REPORTING REQUIREMENTS/DATA AND SAFETY MONITORING PLAN

### 7.1.1 Adverse Event

An adverse event is defined as any untoward medical occurrence in a human subject, including any abnormal sign (for example, abnormal physical exam or laboratory finding), symptom, or disease, temporally associated with the subject’s participation in research, whether or not considered related to the subject’s participation in the research.

#### 7.1.2 Suspected adverse reaction

Suspected adverse reaction means any adverse event for which there is a reasonable possibility that the drug caused the adverse event. For the purposes of IND safety reporting, ‘reasonable possibility’ means there is evidence to suggest a causal relationship between the drug and the adverse event. A suspected adverse reaction implies a lesser degree of certainty about causality than adverse reaction, which means any adverse event caused by a drug.

#### 7.1.3 Unexpected adverse reaction

An adverse event or suspected adverse reaction is considered “unexpected” if it is not listed in the investigator brochure or is not listed at the specificity or severity that has been observed; or, if an investigator brochure is not required or available, is not consistent with the risk information described in the general investigational plan or elsewhere in the current application.

"Unexpected" also refers to adverse events or suspected adverse reactions that are mentioned in the investigator brochure as occurring with a class of drugs or as anticipated from the pharmacological properties of the drug, but are not specifically mentioned as occurring with the particular drug under investigation.

#### 7.1.4 Serious

An Unanticipated Problem or Protocol Deviation is serious if it meets the definition of a Serious Adverse Event or if it compromises the safety, welfare or rights of subjects or others.

#### 7.1.5 Serious Adverse Event

An adverse event or suspected adverse reaction is considered serious if in the view of the investigator or the sponsor, it results in any of the following:

- Death
- A life-threatening adverse drug experience
- Inpatient hospitalization or prolongation of existing hospitalization
- Persistent or significant incapacity or substantial disruption of the ability to conduct normal life functions
- A congenital anomaly/birth defect.
- Important medical events that may not result in death, be life-threatening, or require hospitalization may be considered a serious adverse drug event when, based upon appropriate medical judgment, they may jeopardize the patient or subject and may require medical or surgical intervention to prevent one of the outcomes listed in this definition.

#### 7.1.6 Disability

A substantial disruption of a person’s ability to conduct normal life functions.

#### 7.1.7 Life-threatening adverse drug experience

Any adverse event or suspected adverse reaction that places the patient or subject, in the view of the investigator or sponsor, at immediate risk of death from the reaction as it occurred, i.e., it does not include a reaction that had it occurred in a more severe form, might have caused death.

#### 7.1.8 Protocol Deviation (NIH Definition)

Any change, divergence, or departure from the IRB-approved research protocol.

### 7.1.9 Non-compliance (NIH Definition)

The failure to comply with applicable NIH Human Research Protections Program (HRPP) policies, IRB requirements, or regulatory requirements for the protection of human research subjects.

### 7.1.10 Unanticipated Problem

Any incident, experience, or outcome that:

- Is unexpected in terms of nature, severity, or frequency in relation to
  - (a) the research risks that are described in the IRB-approved research protocol and informed consent document; Investigator’s Brochure or other study documents, and
  - (b) the characteristics of the subject population being studied; **AND**
- Is related or possibly related to participation in the research; **AND**
- Suggests that the research places subjects or others at a *greater risk of harm* (including physical, psychological, economic, or social harm) than was previously known or recognized.

## 7.2 NCI-IRB AND CLINICAL DIRECTOR REPORTING

### 7.2.1 NCI-IRB and NCI Clinical Director Expedited Reporting of Unanticipated Problems and Deaths

The Protocol PI will report in the NIH Problem Form to the NCI-IRB and NCI Clinical Director:

- All deaths, except deaths due to progressive disease
- All Protocol Deviations
- All Unanticipated Problems
- All non-compliance

Reports must be received within 7 days of PI awareness via iRIS.

### 7.2.2 NCI-IRB Requirements for PI Reporting at Continuing Review

To ensure safety using this treatment, the NCI ETIB will review safety data on all protocols semi-annually at the time of continuing review. Data will be presented for both the recent 6 month period and for the entire length of time the protocol has been open. The toxicity data for review will include all toxicities captured on the protocol and will include a table that describes all incidences of intubation including the duration of and reason for intubation.

The protocol PI will report to the NCI-IRB:

1. A summary of all protocol deviations in a tabular format to include the date the deviation occurred, a brief description of the deviation and any corrective action.
2. A summary of any instances of non-compliance
3. A tabular summary of the following adverse events:

- All Grade 2 **unexpected** events that are possibly, probably or definitely related to the research;
- All Grade 3 and 4 events that are possibly, probably or definitely related to the research;
- All Grade 5 events regardless of attribution;
- All Serious Events regardless of attribution.

**NOTE:** Grade 1 events are not required to be reported.

